5.2 Consolidation Therapy Registration

After completing induction therapy, patients will be registered for consolidation treatment provided that they were eligible for the initial registration and satisfy the following additional criteria.

- _____ a. Patients must have achieved A1 marrow status, B1 peripheral blood status and C1 extramedullary disease status (see Section [10.1](#)). Patients must have maintained a B1 peripheral blood status for at least 7 days prior to registration for this protocol step.
- _____ b. For patients affiliated with CALGB or ECOG, collection of cytogenetic specimens must be completed within 8 weeks (preferably within 4 weeks) prior to this registration. Collection and submission of required materials must be by one of the following mechanisms:
- ECOG Sites: See Section [15.3](#).
 - CALGB Sites: See Section [15.4](#).
- _____ c. For all patients, specimens for RT-PCR assays for PML-RAR α must be collected and submitted within 8 weeks (preferably within 4 weeks) prior to this registration. Note that submission of specimens for RT-PCR assays is also required prior to Consolidation Cycle 3. Specimen submissions must be via the mechanisms indicated below.
- SWOG Sites and other sites not affiliated with ECOG or CALGB: Specimens must be submitted to a CLIA-approved laboratory. See Section [15.2](#).
 - ECOG Sites: See Section [15.3](#).
 - CALGB Sites: See Section [15.4](#).

Each of the criteria in the following section must be met in order for a patient to be considered eligible for registration. Use the spaces provided to confirm a patient's eligibility. For each criterion requiring test results and dates, please record this information on the APL Disease Assessment Form and submit to the Data Operations Center in Seattle (see Section [14.0](#)). Any potential eligibility issues should be addressed to the Data Operations Center in Seattle at [name] prior to registration.

SWOG Patient No. _____

Patient's Initials (L, F, M) _____

5.3 Maintenance Therapy Registration

After completing consolidation therapy, patients will be registered for maintenance treatment provided that they were eligible for the consolidation registration and satisfy the following additional criterion:

- _____ a. Patients must remain in A1 marrow status, B1 peripheral blood status and C1 extramedullary disease status (see Section [10.1](#)). Patients must have maintained a B1 peripheral blood status for at least 7 days prior to registration for this protocol step.

- _____ b. For all patients, specimens for RT-PCR assays for PML-RAR α must be collected and submitted within 8 weeks (preferably within 4 weeks) prior to this registration. Specimen submissions must be via the mechanisms indicated below.
 - SWOG Sites and other sites not affiliated with ECOG or CALGB: Specimens must be submitted to a CLIA-approved laboratory. See Section [15.2](#).
 - ECOG Sites: See Section [15.3](#).
 - CALGB Sites: See Section [15.4](#).

6.0 STRATIFICATION FACTORS

There are no stratification factors in this study.

7.0 TREATMENT PLAN

For treatment or dose modification questions, please contact the Study Chair, [name] at [name], or if [name] is not available, [name] at [name]. For dosing principles or questions, please consult the Southwest Oncology Group Policy #38 "Dosing Principles for Patients on Clinical Trials" at <http://swog.org> (then click on "Policies and Manuals" under the "Visitors" menu and choose Policy #38).

7.1 Good Medical Practice

This clinical trial can fulfill its objectives only if patients appropriate for the trial are enrolled. All relevant medical and other considerations should be taken into account when deciding whether this protocol is appropriate for a particular patient. To maximize patient safety, patients should be treated on this protocol only at centers having ready access to blood product support and adequate staff to care for the severely neutropenic patient with multiple-therapy induced toxicities. Physicians should consider the risks and benefits of any therapy, and, therefore, only enroll patients for whom the agents administered are appropriate. Although they will not be considered as formal eligibility criteria, as part of this decision-making process, physicians should recognize that the following problems may increase the risk to the patient entering this protocol. These are guidelines, not strict eligibility criteria. See Section 5.0 for strict eligibility criteria. These guidelines apply to all registration steps (Initial Registration, Consolidation Therapy Registration, and Maintenance Therapy Registration).

- a. Patient should not have other serious illnesses that would limit survival to < 2 years.
- b. Patient should not have psychiatric conditions that would prevent compliance with treatment or informed consent.
- c. Patient should not have uncontrolled or severe cardiovascular or pulmonary disease. This would include history of a recent acute myocardial infarction, congestive heart failure, or active angina.
- d. Abnormalities in measured parameters of hepatic and renal function must be considered as potentially serious obstacles for safe tolerance of the therapy prescribed in this protocol. The degree to which such perturbations are attributable to comorbid disease or are leukemia-related should be considered in the decision to enroll a patient on this protocol.
- e. Patients who become pregnant after registration must be removed from protocol therapy.

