3.0 DRUG INFORMATION

3.1 All Trans Retinoic Acid (Tretinoin) (NSC-122758)

a. DESCRIPTION:

Chemistry: All trans retinoic acid (tRA) is a natural retinol metabolite formed from the intestinal oxidation of B-carotene and from tissue anabolism of retinaldehyde. Both retinol and tRA circulate in the blood in tight association with serum proteins, retinol binding protein for retinol and albumin for tRA. tRA is a major endogenous metabolite of Vitamin A (retinol). tRA induces differentiation and/or growth-inhibition in many tumorigenic cell lines and demonstrates therapeutic efficacy in the treatment of certain leukemias particularly promyelocytic leukemia. It also acts to stimulate clonal proliferation of hematopoietic cells and augments, either directly or indirectly, a variety of immune functions.

b. TOXICOLOGY:

Human Toxicology: The toxicities of tRA closely resemble those of hypervitaminosis A. Cheilitis (80% of patients) and headache (77%) are the most common toxicities of tRA usage. Other toxicities include visual disturbances, dryness of mucous membranes, pruritis, dry skin, peeling, fatigue and epistaxis in 10 - 50% of patients. 10% or less of patients develop musculoskeletal pain, conjunctivitis and psychological changes. The CNS toxicity appears dose-related, occurring in 4% or less when tRA is administered at 30 mg/day, but occurring in 50% when tRA is administered at 70 - 100 mg/day. Increases in SGOT/SGPT/bilirubin, triglycerides, cholesterol and fibrinogen have also been seen. All trans retinoic acid has been associated with cases of pseudotumor cerebri.

Skeletal changes have been reported in adults receiving prolonged treatment with cis retinoic acid (cRA). Whether these effects accompany tRA administration of long term is not well defined. In APL patients treated with tRA, 55% developed hypertriglyceridemia and 40% manifested increased liver transaminases. Patients with APL have also experienced hyperleukocytosis and a cardio-pulmonary syndrome.

Like cRA, tRA must be considered a teratogen, and may potentially cause craniofacial abnormalities, CNS abnormalities, thymic aplasia and cardiac abnormalities. It is considered a class C FDA pregnancy risk since animal studies have shown adverse effects and toxicities on the fetus. No adequate or well-controlled studies have been done on pregnant women.

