 - CALGB Sites: CALGB patients must be registered on **CALGB 8461** PRIOR to registration to **S0535**. The CALGB patient number will be required by CTSU at the time of **S0535** registration (see Section [15.4](#)).

SWOG Patient No. _____

Patient's Initials (L, F, M) _____

- _____ g. For all patients, pretreatment specimens for baseline RT-PCR assays for PML-RAR α must be collected and submitted within 14 days prior to registration to **S0535**. Note that there are also additional time points at which specimens are required to be submitted for RT-PCR assays (see Section [15.0](#)). Specimen submissions must be via the mechanisms indicated below. Repository aspects of the ancillary protocols for CALGB and ECOG are optional as outlined in the informed consent documents.
- SWOG and CALGB Sites and other sites not affiliated with ECOG: Specimens must be submitted to a CLIA-approved laboratory. See Sections [15.2](#) and [15.4](#).
 - ECOG Sites: Pretreatment specimens of marrow and/or peripheral blood must be submitted to the Leukemia Translational Studies Laboratory (LTSL) at Our Lady of Mercy Cancer Center, New York via **E3903**, "Ancillary laboratory protocol for collecting diagnostic material on patients considered for ECOG treatment trials for Leukemia or related hematologic disorders". Register patient to **E3903** PRIOR to registration to **S0535**. The ECOG patient number will be required at the time of **S0535** registration. See Section [15.3](#).
 - CALGB Sites: CALGB patients must be offered participation on **CALGB 9862**. Consenting patients must be registered to **CALGB 9862** PRIOR to registration to **S0535** (see Section [15.4](#)).
- _____ h. Patients must not be pregnant or nursing because ATRA as well as other drugs used in this protocol may cause fetal harm and because of the potential for serious adverse reactions in nursing infants from the drug. Women of childbearing potential must have a negative pregnancy test performed within 14 days prior to registration. Women/men of reproductive potential must have agreed to use an effective contraceptive method.
- _____ i. No other prior malignancy is allowed except for the following: adequately treated basal cell or squamous cell skin cancer, in situ cervical cancer, adequately treated Stage I or II cancer from which the patient is currently in complete remission, or any other cancer from which the patient has been disease-free for 5 years.

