7.11 Criteria for Removal from Protocol Treatment

- a. Patients whose pretreatment RT-PCR assays are found to be PML-RAR α -negative will be removed from protocol treatment and receive no further treatment under this protocol (see Section [7.3d](#)).
- b. Delay of more than 5 days prior to initiation of gemtuzumab ozogamicin during induction.
- c. Patients who fail to achieve A1 marrow, B1 blood, and C1 extramedullary disease status (see Section [10.1](#)) within 90 days of initiation of induction therapy will not be eligible for consolidation therapy and will receive no further treatment under this protocol.

- d. Unacceptable toxicity as defined in Section [8.0](#).
- e. Patients who do not maintain CR or relapse before or while receiving consolidation or maintenance therapy.
- f. Patients who become pregnant.
- g. Successful completion of all stages of therapy.
- h. The patient may withdraw from the study at any time for any reason.

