9.0 STUDY CALENDARS

REQUIRED STUDIES	PRE-STUDY	INDUCTION	CONSOLIDATION #1 through 2		CONSOLIDATION #3 through 4		CONSOLIDATION #5 through 6		MAINTENANCE		Follow Up
			Prior	During	Prior	During	Prior	During	Prior	During	
PHYSICAL											
History & Physical Exam	X	2X/week	X	X&	X	X α	X	X&	X	X&	X√
Height, Weight and BSA	X		X	X†	X	X†	X	X†	X	X&	X√
Performance Status (Zubrod)			X	X&	X	X α	X	X&	X	X&	X√
Toxicity Notation		2X/week	X		X		X		X	X&	X√
LABORATORY STUDIES											
CBC, Diff, Plts	X	2X/week	X	weekly	X	weekly	X	weekly	X	X&	X√
Pregnancy test	X										
Electrolytes (incl. Ca ⁺ and Mg ⁺⁺), creatinine *	X	2X/week	X	weekly	X	weekly	X	weekly	X	X&	
Bilirubin, AST, ALT, Alkaline phosphatase *	X	2X/week	X	weekly	X	weekly	X	weekly	X	X&	
Cholesterol, triglycerides *	X				X		X		X	X&	
PTT, PT, fibrinogen, FDP, D-dimer Δ *	X	2X/week									
BM Aspirate/Biopsy ⊖	X	X ψ	X		X				X	XΠ	X
Cytogenetics Σ	X	X ú									X¿
RT-PCR for PML-RARα Σ	X	X			X†				X		X¿
Lumbar Puncture (see Section 7.2b)			X								
X-RAYS AND SCANS											
Chest X-Ray %	X										
MUGA/ECHO					X#						
EKG \$	X	2X/week			X						
TREATMENT (See Section 7.0)											
Allopurinol/rasburicase		X									
ATRA		X f				X				X	
Daunomycin						X					
Arsenic trioxide		X		X							
6-mercaptopurine										X	
Methotrexate										X	
Gemtuzumab ozogamicin		X						X			

NOTE: Forms are found in Section 18.0. Forms submission guidelines are found in Section 14.0.

Click here to view [footnotes](#).

Footnotes:

- * Results of these tests do not determine eligibility but should be done prior to registration in accordance with good medical practice.
- & Monthly.
- √ After the patient is off treatment, the remaining of Months 3, 6, 9, 12, 18, 24 and 36 from the time of initial registration.
- Δ These tests should be done at pretreatment, twice weekly during induction until normal, and as clinically indicated thereafter.

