13.1 Registration Timing

Patients must be registered prior to initiation of Induction (Step 1—Initial Registration), Consolidation (Step 2—Consolidation Therapy Registration), or Maintenance (Step 3—Maintenance Therapy Registration) treatment no more than one working day prior to planned start of treatment.

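### No pregnancy test is scheduled after entry, although teratogenic or fetotoxic drugs start or restart months later and the removal rule depends on knowing of a pregnancy

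*Combined protocol and SAP*

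**What the plan says.** Section 5.1h sets the entry requirement: "Women of childbearing potential must have a negative pregnancy test performed within 14 days prior to registration". Its reason is that "ATRA as well as other drugs used in this protocol may cause fetal harm". It also requires agreement to use effective contraception.

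After entry the protocol has a removal rule but no scheduled test:

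- Section 7.1e: "Patients who become pregnant after registration must be removed from protocol therapy". Section 7.11f lists "Patients who become pregnant" among the criteria for removal from protocol treatment.
- Section 9.0: the row labelled "Pregnancy test" is marked in the pre-study column only and carries no footnote.
- Sections 5.2 and 5.3, the criteria for consolidation and maintenance registration, do not ask for a repeat test.
- Section 16.1i requires expedited reporting of a pregnancy on study.

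The drug sections describe the hazard. Section 3.1b says "tRA must be considered a teratogen, and may potentially cause craniofacial abnormalities". Section 3.3b calls daunomycin teratogenic, 3.4b warns of fetal harm from gemtuzumab, and 3.6b records fetal deaths and congenital anomalies with methotrexate. Section 3.1b also strongly recommends, without requiring, a pregnancy test in the two weeks before ATRA therapy.

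**The concern.** The reason that 5.1h gives for the entry test applies again at three later points: Cycles 3-4 (ATRA restarts, daunomycin starts), Cycles 5-6 (gemtuzumab restarts) and maintenance (ATRA restarts, methotrexate starts). If a test no more than 14 days old is the standard before first exposure, the plan gives no reason for accepting one that is months old before these later exposures.

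The removal and reporting rules act only once a pregnancy is known. With no scheduled test, an early and unsuspected pregnancy could be exposed before either rule applies. What is at stake is possible irreversible fetal harm. The sample size, significance level, power and endpoints are not affected.

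**Working it through.** The documents give no figure for the age of the test, so there is none to reproduce. I summed the protocol's own intervals from the entry test to Day 1 of Cycle 3, taking registration and the start of induction as the same day (13.1 allows at most one working day between them).

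| Interval | Source | Low (days) | High (days) |
|---|---|---|---|
| Test to registration | 5.1h | 0 | 14 |
| Induction to CR | Day 42 marrow in 7.8a and 9.0; 90-day limit in 7.11c | 42 | 90 |
| CR to Cycle 1 | 7.4a | 0 | 56 |
| Cycle 1 | 7.4b | 35 | 35 |
| Rest | 7.4b | 14 | 14 |
| Cycle 2 | 7.4b | 35 | 35 |
| Cycle 2 to Cycle 3 | 7.5a | 0 | 28 |
| **Total** | | **126** | **272** |

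- With Cycles 1-2 given: 126/7 = 18.0 weeks to 272/7 = 38.9 weeks.
- With Cycles 1-2 skipped because arsenic was stopped for good in induction (8.4d), and assuming 0-8 weeks from CR to Cycle 3: 42/7 = 6.0 weeks to (14 + 90 + 56)/7 = 160/7 = 22.9 weeks.

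**Sensitivity of the lower end.** Section 7.8a allows a marrow earlier than Day 42 if neutrophils recover.

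- CR at Day 28 (assumed): (28 + 84)/7 = 16.0 weeks, or 4.0 if Cycles 1-2 are skipped.
- CR at Day 42 plus the seven days of stable counts required by 5.2a: (42 + 7 + 84)/7 = 19.0 weeks, or 7.0.
- Day 42 counted from ATRA begun five days before registration: (37 + 84)/7 = 17.3 weeks, or 5.3.

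**Upper end.** The four-week limit before Cycle 3 in 7.5a is a target, so 38.9 weeks is not a strict maximum.

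**Later starts, lower bounds only.** Each adds the two-week minimum gap (7.5b, 7.6a, 7.6b, 7.7a) and no time for count recovery.

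| Start | Cycles 1-2 given (weeks) | Cycles 1-2 skipped (weeks) |
|---|---|---|
| Cycle 4 | 18 + 2 = 20 | 6 + 2 = 8 |
| Cycle 5 | 22 | 10 |
| Cycle 6 | 24 | 12 |
| Maintenance | 26 | 14 |

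The documents give no recovery time for this population, so I set no upper bounds here.

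**Do the registration steps supply a check?** Section 7.1 says: "These guidelines apply to all registration steps (Initial Registration, Consolidation Therapy Registration, and Maintenance Therapy Registration". Section 13.1 ties each registration to the start of its phase: "treatment no more than one working day prior to planned start of treatment". The only later registrations are therefore before Cycle 1 and before maintenance. The consolidation registration falls 5 + 2 + 5 = 12 to 12 + 4 = 16 weeks before Cycle 3 unless Cycles 1-2 are skipped, and no registration comes between it and Cycle 5. Neither step requires a test in any case.

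**The case against.** The strongest reply is that the protocol has more protection than the calendar row suggests. Contraception is required at entry (5.1h) and advised throughout ATRA therapy (3.1b). The daunomycin, gemtuzumab and methotrexate sections each carry a pregnancy caution for women of childbearing potential. History and physical examination are scheduled before each treatment block and during it. The test recommended in 3.1b can be read as covering every ATRA restart. On that reading, three of the five proposed tests (Cycles 3 and 4, and maintenance) are already recommended, and only Cycles 5-6 have no testing text at all.

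This narrows the gap without closing it. The 3.1b wording is not mandatory, is absent from the calendar, does not say whether it covers restarts, and cannot cover cycles in which gemtuzumab is the only drug. Contraception and advice lower the risk but detect nothing, and examination can miss an early pregnancy.

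The following objections stand as limits:

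- The age of a test is not a probability of pregnancy.
- The model consent form and the package inserts, to which Section 3 refers sites, were not available and may say more.
- Sections 7.1e and 7.11f apply at any time after registration. The 12-16 week figure shows only that registration supplies no check near Cycle 3; it does not limit the removal rule.
- Testing at cycle starts, while relying on history and examination within the maintenance year, is a judgement. It matches the entry rule of testing before exposure starts, but other schedules are defensible.

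**Conclusion.** The concern holds. No pregnancy test is scheduled after entry, and the one required test is about 18-39 weeks old when ATRA restarts and daunomycin begins, or about 6-23 weeks if Cycles 1-2 are skipped. The lower ends assume CR at Day 42. The skipped-cycle range also assumes 0-8 weeks from CR to Cycle 3.

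The calendar fact and the interval sums are firm. The number of women of childbearing potential is not given, so I do not estimate expected pregnancies or fetal exposures. This is a gap in safety monitoring that should be corrected; it is not a breach of a stated requirement.

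**What to change.** In the pregnancy-test row of Section 9.0, add a mark in the Prior columns for Consolidation 3-4, Consolidation 5-6 and Maintenance, with this footnote: women of childbearing potential only; test within 14 days before Day 1 of each of Consolidation Cycles 3, 4, 5 and 6 and before Day 1 of maintenance, but not before each 14-day maintenance ATRA course. During the maintenance year the monthly history and examination remain the check.

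The cost is up to five assays per woman of childbearing potential, at points where blood counts and chemistry are already scheduled, so no extra visit is needed. For 70 eligible patients and an assumed 20-40% share, that is 70 × 0.20 × 5 = 70 to 70 × 0.40 × 5 = 140 assays, fewer after early deaths and withdrawals. The 2-8 week start windows before Cycles 4, 5, 6 and maintenance leave time to repeat a doubtful result. The edit is one row and one footnote, but it would go out as a numbered revision subject to IRB handling. The study is marked closed effective June 2013, so the main use now is to correct the plan and to inform similar protocols.

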7.2 General Considerations

- a. Immediate measures to diagnose and begin treatment of infections should be instituted prior to induction therapy.
- b. A lumbar puncture is recommended following completion of induction, but not required. Prophylactic intrathecal chemotherapy may be given at the treating physician's discretion.
- c. All patients should be carefully followed serially with coagulation studies (PTT, PT, fibrinogen, FDP, and D-dimer). These tests should be done pretreatment, twice weekly during induction until normal and as clinically indicated thereafter. Optimal management of coagulopathy is controversial. Heparin usage is discouraged since all patients will be receiving ATRA; however, patients with either biochemical or clinical evidence of coagulopathy may be treated at the investigator's discretion.

- d. Additional electrolyte studies for calcium, magnesium, cholesterol and triglycerides should be obtained.
- e. Hydroxyurea therapy is permitted up to 24 hours before initiation of gemtuzumab ozogamicin (G.O.).
- f. All patients will be started on allopurinol 300 mg/day orally. For patients allergic to allopurinol, rasburicase may be substituted. Reversible abnormalities of metabolic function should be treated aggressively and corrected prior to institution of therapy.
- g. Investigators may contact the SWOG Study Chairs or Leukemia Committee Chair for assistance with the management of patients with high WBC count prior to confirmation of molecular diagnosis.

7.3 Induction Chemotherapy

AGENT	DOSE	ROUTE	Time	NOTES
ATRA ^ζ	45 mg/m ² /day (in 2 doses, 22.5 mg/m ² every 12 hours)	PO	every 12 hrs, Day 1 to CR *	With food. See Section 7.3a below.
Gemtuzumab Ozogamicin ^Δ	9 mg/m ²	IV infusion over 2 hours	Day 1 only ^π	
Arsenic Trioxide	0.15 mg/kg/d	IV infusion over 2 hours	5 days/wk beginning on Day 10 and continuing until CR ^ψ	

* For maximum of 90 days, unless prohibited by either unacceptable toxicity or progressive disease.

^π G.O. may be delayed until Day 6 pending confirmation of APL diagnosis by FISH/cytogenetics, or RT-PCR. Hydroxyurea may be utilized during this time, up to 24 hours prior to initiation of gemtuzumab ozogamicin.

^ψ For a maximum of 60 days, unless prohibited by either unacceptable toxicity or progressive disease.

^Δ Recommended premedications prior to gemtuzumab: acetaminophen 1 gm orally, diphenhydramine 50 mg IV, and methylprednisolone 125 mg IV.

^ζ Day 1 of treatment will be the first day the patient is treated with ATRA, regardless of patient's registration status.

a. ATRA will be "rounded" up to the nearest 10 mg, divided into 2 daily doses, given orally every 12 hours with food.

b. **ATRA syndrome:** A spectrum of clinical manifestations of a cardiorespiratory distress syndrome has been described, including respiratory distress, hypoxemia, fever, erythematous rash, pulmonary infiltrates, pleural or pericardial effusions, congestive heart failure with impaired myocardial contractility and episodic hypotension. Patients with this syndrome may develop rapidly progressive cardiopulmonary failure.

If this syndrome is suspected, ATRA should be held and dexamethasone 10 mg IV or PO BID will be given for 3 days. ATRA will be resumed once the signs/symptoms of the syndrome have resolved. Patients with persistent signs/symptoms of the ATRA syndrome after 3 days of dexamethasone or who have recurrence of the ATRA syndrome after restarting ATRA should be discussed with the Study Chair.

- c. **Prolonged QT_c:** Prolongation of the QT_c has been reported with the use of arsenic trioxide in association with electrolyte abnormalities. Therefore, any identified electrolyte abnormalities of potassium, calcium, or magnesium should be promptly corrected to within normal limits prior to and during treatment with arsenic trioxide. EKG must be obtained twice weekly during induction therapy and as clinically indicated.
- d. Patients may be registered on this study and begin induction chemotherapy before the result of the required pretreatment RT-PCR assay for PML-RAR α is available (see Section 5.1b). If the patient is found to be PML-RAR α -negative, then the patient is removed from protocol treatment and should receive appropriate chemotherapy for non-APL acute myeloid leukemia.

7.4 Consolidation Cycles 1 and 2

- a. Patients who achieve A1 bone marrow, B1 peripheral blood, and C1 extramedullary disease status (see Section 10.1) may be eligible for registration to consolidation therapy (see Section 5.2). Consolidation Cycle 1 therapy should be started within 4 weeks and no later than 8 weeks following documentation of CR.

- b. Consolidation Cycles 1 and 2 Treatment Plan

AGENT	DOSE	ROUTE	Time	NOTES
Arsenic Trioxide	0.15 mg/kg/day	IV over 2 hours	5 days/week x 5 weeks	Repeat after 2 weeks rest*

* Consolidation Cycle 2 may be given after 2 weeks of rest following Cycle 1.

- c. **Prolonged QT_c:** Prolongation of the QT_c has been reported with the use of arsenic trioxide in association with electrolyte abnormalities. Therefore, any identified electrolyte abnormalities of potassium, calcium, or magnesium should be promptly corrected to within normal limits prior to and during treatment with arsenic trioxide.
- d. MUGA or echocardiogram must be performed prior to initiation of Consolidation Cycle 3 (see Section 7.5c). If the test has been performed at baseline or any time prior to Consolidation Cycle 3, it does not need to be repeated immediately before Cycle 3.

7.5 Consolidation Cycles 3 and 4

- a. Patients who remain in A1 bone marrow, B1 peripheral blood, and C1 extramedullary disease status (see Section 10.1) may continue consolidation therapy. Consolidation Cycle 3 should be started within 4 weeks following completion of Consolidation Cycle 2 if possible.
- b. Consolidation Cycle 4 should be started no earlier than 2 weeks, and no later than 8 weeks from recovery to B1 peripheral blood status.
- c. MUGA or echocardiogram must be performed prior to initiation of Consolidation Cycle 3. If the test has been performed at baseline or any time prior to Consolidation Cycle 3, it does not need to be repeated immediately before Cycle 3. EKG should be obtained as clinically indicated thereafter.
- d. Patients who cannot receive daunomycin because of cardiac or other toxicity, or are unable to initiate Consolidation Cycle 4 within 8 weeks of recovering peripheral blood counts to B1 status, must be discussed with the Study Chair; if in CR, these patients will proceed to Consolidation Cycle 5.

e. Consolidation Cycles 3 and 4 Treatment Plan

AGENT	DOSE	ROUTE	Time	NOTES
ATRA	45 mg/m ² /day (in 2 doses, 22.5 mg/m ² every 12 hours)	PO	every 12 hours, Days 1-7	With food. See Section 7.5e below.
Daunomycin*	50 mg/m ² /day	IV bolus or 1 hour infusion	Days 1-3	

* Idarubicin, 12mg/m²/day, on Days 1-3, may be used in place of daunomycin only if daunomycin is unavailable due to the national shortage. This must be documented on the **S0535** Consolidation Cycles 3 and 4 Treatment Summary Form.

- f. ATRA will be “rounded” up to the nearest 10 mg, divided into 2 daily doses, given orally every 12 hours with food.
- g. Prior ATRA syndrome: Patients who experienced the ATRA syndrome during induction may receive ATRA during Consolidation Cycles 3 and 4, since the ATRA syndrome is not expected to occur during remission.

7.6 Consolidation Cycles 5 and 6

- a. Patients who remain in B1 peripheral blood, and C1 extramedullary disease status (see Section [10.1](#)) may continue consolidation therapy. Consolidation Cycle 5 should be started no earlier than 2 weeks and no later than 8 weeks after recovery of peripheral blood counts to B1 status (see Section [10.1](#)).
- b. Consolidation Cycle 6 should be started no earlier than 2 weeks, and no later than 8 weeks after recovery to B1 peripheral blood status.
- c. Patients who cannot receive gemtuzumab ozogamicin because of previous toxicity or who are unable to initiate Consolidation Cycle 6 within 8 weeks after recovering peripheral blood counts to B1 status must be discussed with the Study Chair; if in CR, these patients will proceed to Maintenance Therapy.
- d. Consolidation Cycles 5 and 6 Treatment Plan

AGENT	DOSE	ROUTE	Time	NOTES
Gemtuzumab Ozogamicin ^Δ	9 mg/m ²	IV infusion over 2 hours	Day 1	

^Δ Recommended premedications prior to gemtuzumab: acetaminophen 1 gm orally, diphenhydramine 50 mg IV, and methylprednisolone 125 mg IV.

